If the lab results are found to be abnormal (AST/ALT > 2x upper limit of normal, serum creatinine > 1.2 mg/dl, TSH outside normal limits), we will ask the study participants to discontinue study medication for 2 weeks. After 2 weeks, we will ask them to come for an interim study visit and draw their blood for liver function tests, renal function tests and thyroid function tests. If lab values have returned to within study's acceptable limits (AST/ALT < 2x upper limit of normal, serum creatinine < 1.2 mg/dl, TSH within normal limits), and as advised by the study Data Safety Monitoring Board, we will then ask them to resume the study medication.

After 2 weeks, if the lab tests are still abnormal (AST/ALT > 2x upper limit of normal; serum creatinine > 1.2 mg/dl; TSH outside normal limits), then the study participants will discontinue study medication permanently (although we will ask them continue to be followed up in the study).

- 3. 15 week visit (end of double blind Phase 1):** Enrolled subjects will then be asked to come for their 15 week (follow-up) study visit, where OACIS-I, SRS, ABC and Vineland Adaptive Behavior Scale will be administered. A complete physical examination will be performed and vital signs obtained. This visit will take ~ 1.5 hours to complete. They will be asked about any serious side effects they might have experienced. Also, clinical laboratory tests (CBC and platelets, complete metabolic profile (including liver function tests, renal function tests, thyroid function tests), and research laboratory tests blood- (Nrf2, heat shock proteins, measures of oxidative stress and mTOR) and urine sample for isoprostanes will be obtained. Maximum amount of blood drawn at any stage during this study will not exceed 2 ml/kg body weight; we will also not exceed the minimal risk limitation of 3 ml/kg in an 8 week period.

At this visit, we will give the study participants a further 8 week supply of study medication (sulforaphane) that will last until the next (22 week) visit plus a one-week buffer. We will provide detailed instructions for subjects/parents/guardians on how to take the study medication along with the medication package, and they will be made aware (and given written instructions) on how to recognize any side effects associated with the study medication. They will be asked to call the study staff in case they have any questions or concerns.

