If at this visit lab results are found to be abnormal (AST/ALT > 2x upper limit of normal, serum creatinine > 1.2 mg/dl, TSH outside normal limits), we will ask the study participants to discontinue study medication for 2 weeks. After 2 weeks, we will ask them to come for an interim study visit and draw their blood for liver function tests, renal function tests and thyroid function tests. If lab values have returned to within study's acceptable limits (AST/ALT < 2x upper limit of normal, serum creatinine < 1.2 mg/dl, TSH within normal limits), and as advised by the study Data Safety Monitoring Board, we will then ask them to resume the study medication.

After 2 weeks, if the lab tests are still abnormal (AST/ALT > 2x upper limit of normal; serum creatinine > 1.2 mg/dl; TSH outside normal limits), then the study participants will discontinue study medication permanently (though we will ask them continue to be followed-up in the study).

- 4. 22 week visit (open label Phase 2):** Enrolled subjects will then be asked to come for their 22 week (follow-up) study visit, where OACIS-I, SRS, ABC and Vineland Adaptive Behavior Scale will be administered. A complete physical

examination will be performed and vital signs obtained. This visit will take ~ 1.5 hours to complete. They will be asked about any side effects they might have experienced. Also, clinical laboratory tests (CBC and platelets, complete metabolic profile (including liver function tests, renal function tests, thyroid function tests), and research laboratory tests blood- (Nrf2, heat shock proteins, measures of oxidative stress and mTOR) and urine sample for isoprostanes will be obtained. Maximum amount of blood drawn at any stage during this study will not exceed 2 ml/kg body weight; we will also not exceed the minimal risk limitation of 3 ml/kg in an 8 week period.

At this visit, we will give the study participants a further 7 week supply of study medication (sulforaphane) that will last until the next (30 week) visit. We will provide detailed instructions for subjects/parents/guardians on how to take the study medication along with the medication package, and they will be made aware (and given written instructions) on how to recognize any side effects associated with the study medication. They will be asked to call the study staff in case they have any questions or concerns.

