Risk management and emergency response: Risks to subjects will be minimized by close follow-up and consideration of all reported symptoms and concerns of parents, guardians and caregivers. Regular examinations and laboratory testing of blood counts and serum chemistries, including liver function tests, renal function tests, and thyroid function tests will be performed at the screening visit, 7 week, 15 week, 22 week, 30 week and 36 week visits, and reviewed by the study team and Data Safety Monitoring Board. The PI or physician colleague will be on call 24/7 for any concerns of adverse events during the study. Risks of phlebotomy will be reduced by behavioral preparation, use of topical anesthetic and carried out by phlebotomists experienced in working with persons with autism. Protection of subjects will include confidential treatment of all health related information, and all research data will be coded, the reference codes to be maintained under lock and key by the PI and study coordinator at all times.

If lab signs of toxicity are found (AST/ALT > 2x upper limit of normal; serum creatinine > 1.2 mg/dl; TSH outside normal limits), the patient will discontinue study medication for 2 weeks before resuming the study medication, once lab values return to within study's acceptable limits. At the end of 2 weeks, we will do lab tests again. If at that time, lab tests are still not within study's acceptable limits (AST/ALT > 2x upper limit of normal; serum creatinine > 1.2 mg/dl; TSH outside normal limits), subjects will discontinue permanently the study medication (though they will still continue to be followed-up in the study). Lab tests are required at screening, 7-week, 15-week, 22 week, 30 week and closeout visits: Hematology and complete metabolic profile (including liver, kidney, thyroid function tests); urinalysis for protein and hemoglobin. Possible clinical side effects of sulforaphane will be monitored, including: GI disturbances (flatulence, soft stool, and large bowel movement), and frequent urination⁶³. Staff members will be available 24/7 for emergencies. Maximum amount of blood drawn at any stage during this study will not exceed 2 ml/kg body weight; also we will not exceed the minimal risk requirements of 3ml/kg in an 8 week period.

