If any child in the study has a seizure while taking the medication, the study drug will be discontinued and study physicians and Data Safety Monitoring Board (DSMB) will be notified. The child will be evaluated by [name] or his designee, pediatrician or family doctor, and treated and followed up appropriately for the duration of the study. We will ask the parents to return with the child for repeat safety lab studies and to return unused study drug.

In the event of significant shifts in behavior, based on the family's experience and judgment, the child will be examined by the study physician(s) or the child's pediatrician, the study drug will be temporarily discontinued for 2 weeks and DSMB notified. If the behavior(s) subside, the medication will be resumed on the previous schedule. Since

children with ASD often have cyclic behavior changes without respect to the medications they are taking, we will rely primarily on the caregivers' experience in assessing whether the behavior(s) in question are out of the norm for their child. However, we will be cautious in evaluating the child for possible medical reasons for the change in behavior (e.g., gastrointestinal discomfort, disordered sleep). If adverse behaviors do not subside after 2 weeks and no medical cause for the behaviors is found, the study medication may be restarted if the DSMB, study physicians and the parents agree. Otherwise, medication will not be restarted and we will ask that the family return the remaining study drug supply.

We will constitute study drug pause and study drug stop rules based on objectively measurable criteria. These criteria appear below:

Subject Drug Pause Criteria: Subjects will be asked to stop taking study medication for 2 weeks if:

1. At 7 week visit, subjects reported any serious side effects and subsequent laboratory tests are outside of study's acceptable limits - liver function tests (AST/ALT > 2x upper limit of normal); renal function tests (serum creatinine > 1.2 mg/dl); thyroid function tests (TSH outside normal limits).
2. At 15 week visit, subjects reported any serious side effects and subsequent laboratory tests are outside of study's acceptable limits - liver function tests (AST/ALT > 2x upper limit of normal); renal function tests (serum creatinine > 1.2 mg/dl); thyroid function tests (TSH outside normal limits).

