3. At any time during the study, subjects reported any serious side effects and subsequent laboratory tests are outside of study's acceptable limits - liver function tests (AST/ALT > 2x upper limit of normal); renal function tests (serum creatinine > 1.2 mg/dl); thyroid function tests (TSH outside normal limits).
4. There is a potential interaction of study medication with another medication a subject is taking. We will ask the subject to temporarily stop taking study medication if the other drug is a short term medication (e.g., a course of antibiotics, or prednisone).
5. Intercurrent illness (e.g., infection, asthma, accident or serious injury), requiring medical attention (e.g., emergency room visit or hospital admission). All such incidents will be reviewed with study physicians and the DSMB as they arise, and we will consult with the child's physician regarding the advisability of pausing the study drug and continuing follow up of the child's illness.
6. In the event of significant shifts in behavior, based on the family's experience and judgment, the child will be examined by the study physician(s) or the child's pediatrician, the study drug will be temporarily discontinued for 2 weeks and DSMB notified. If the behavior(s) subside, the medication will be resumed on the previous schedule. Since children with ASD often have cyclic behavior changes without respect to the medications they are taking, we will rely primarily on the caregivers' experience in assessing whether the behavior(s) in question are out of the norm for their child. However, we will be cautious in evaluating the child for possible medical reasons for the change in behavior (e.g., gastrointestinal discomfort, disordered sleep). If adverse behaviors do not subside after 2 weeks and no medical cause for the behaviors is found, the study medication may be restarted if the DSMB, study

physicians and the parents agree. Otherwise, medication will not be restarted and we will ask that the family return the remaining study drug supply.

Subject Drug Stop Criteria: At the end of 2 weeks, we will do lab tests again. At that time, subjects will discontinue the study medication permanently if:

1. Subsequent laboratory tests repeated after 2 weeks are outside of study's acceptable limits - liver function tests (AST/ALT > 2x upper limit of normal); renal function (serum creatinine > 1.2 mg/dl); thyroid function (TSH outside normal limits).

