2. At any point of the study, extreme exacerbation of behavioral symptoms is noted, as above and these behaviors do not subside after 2 weeks of study drug stoppage and no medical cause for the change in behavior is apparent (e.g., gastrointestinal discomfort, disordered sleep).
3. If any child in the study has a seizure while taking the medication, the study drug will be discontinued and study physicians and Data Safety Monitoring Board (DSMB) will be notified. The child will be evaluated by [name] or his designee, pediatrician or family doctor, and treated and followed up appropriately for the duration of the study. We will ask the parents to return with the child for repeat safety lab studies and to return unused study drug.
4. At any time, if there is an interaction of study medication with another long term medication a subject is taking: In a case in which the other drug is the one which a subject is likely to require for a long period of time, subjects will discontinue study medication permanently if there is a possibility of adverse effects as a result of an interaction with that drug (for example, appearance of extrapyramidal signs in a subject taking risperidone).

Data Safety Monitoring Board: An independent data safety management board of 3 persons will be constituted to evaluate the continued safety of sulforaphane. This DSMB will consist of one pediatrician (from the department of Pediatrics at UMass Medical School), one child psychiatrist (from the department of Psychiatry at UMass Medical School) and one bio-statistician (from the department of Quantitative Sciences at UMass Medical School). This DSMB will meet twice a year and review all safety information collected in the past 6 months.

14) **Withdrawal of Subjects***

See study drug pause and stop criteria above.

15) **Risks to Subjects***

Sulforaphane Safety:

Cruciferous vegetables, including broccoli sprouts, are generally regarded as safe and are regular dietary components in many regions of the world. Previous estimates of the daily dietary intake of cruciferous vegetables vary regionally, averaging 40 g/day in Singapore⁶⁴, 11 g/day in the United States⁶⁵, 16 g/day in Canada⁶⁶, 30 g/day in the UK⁶⁷, and 112 g/day in Japan⁶⁸. There have been numerous adult human and animal studies

assessing the safety of sulforaphane. These studies are summarized in the safety and efficacy section of the Investigator Brochure.

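### The drug-pause list in section 13 is narrower than the labs-only pause ordered elsewhere; restart and stop rules overlap for extreme behavior; week-36 safety labs are stated both ways

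*Combined protocol and SAP*

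**What the plan says.** **Pausing on labs.** In section 10, the 7-week visit text gives the limits (AST/ALT above twice the upper limit of normal, and then "serum creatinine > 1.2 mg/dl, TSH outside normal limits), we will ask the study participants to discontinue study medication for 2 weeks"). The 15- and 22-week visits repeat the rule, opening with "If at this visit lab results are found to be abnormal". Section 13, under risk management, says that when lab signs of toxicity appear "the patient will discontinue study medication for 2 weeks before resuming the study medication, once lab values return" to acceptable limits. None of these four statements mentions symptoms.

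Section 13 then sets out a headed list of Subject Drug Pause Criteria:

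- Item 1: "At 7 week visit, subjects reported any serious side effects and subsequent laboratory tests are outside of study's acceptable limits".
- Item 2: "At 15 week visit, subjects reported any serious side effects and subsequent laboratory tests are outside of study's acceptable limits".
- Item 3: "At any time during the study, subjects reported any serious side effects and subsequent laboratory tests are outside of study's acceptable limits".

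The lab limits are the same; the serious side effect is an added condition. Section 14, on withdrawal, contains a single line: "See study drug pause and stop criteria above".

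**Behavior.** Section 13 and Pause Criterion 6 cover a behavioral shift that has not settled after 2 weeks off drug and has no medical explanation. In that case "the study medication may be restarted if the DSMB, study physicians and the parents agree"; otherwise drug stays off. Stop Criterion 2 covers an extreme exacerbation under the same two conditions and requires permanent discontinuation.

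**Week 36.** Section 13 (risk management) includes the final visit in the safety-lab schedule twice. The section 8 timeline and three places in section 10 (the safety-monitoring schedule, the end-of-Phase-3 description and the 36-week visit text) either limit week-36 blood to research tests or end routine labs at week 30.

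**The concern.** Scheduled safety labs exist to find abnormalities that produce no symptoms. A pause list that also requires a reported serious side effect misses those children if it is read alone. It is introduced as the trial's pause and stop rules, and section 14 offers nothing else, so site staff or a monitor may well work from it. The same result could then be handled, or cited as a deviation, in two ways.

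The behavior clauses raise the same problem for a child with an extreme, unresolved exacerbation. At week 36 the open question is whether the trial has any laboratory check after drug has been stopped.

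Safety is Specific Aim 2, and section 15 acknowledges that no earlier study was designed to test the safety of sulforaphane in children. The rules should therefore give one answer.

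**Working it through.** The plan gives no figure to reproduce. The check compares the texts, with a short calculation of blood volume for the fix.

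**1. Pause rule, by case**

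| Child at a lab check | Labs-only rule (section 10, weeks 7, 15, 22; section 13 risk management) | Pause Criteria 1–3 |
|---|---|---|
| Labs out of limits, serious side effect reported | Pause | Pause |
| Labs out of limits, no serious side effect | Pause | Not listed |
| Labs within limits, serious side effect reported | No lab pause | Not listed |

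The rules differ only in the second row. Every child who meets Criteria 1–3 already meets the labs-only rule, so Criteria 1–3 are redundant beside it and too narrow if used alone. The count is four labs-only statements against three criteria with the added condition. Stop Criterion 1, applied at the 2-week repeat, is itself labs-only, which suggests that the symptom condition was not intended.

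**2. Restart against stop**

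Both clauses need two conditions: behavior not settled after 2 weeks off drug, and no medical cause. Under those conditions the restart clause permits resumption if three parties agree. Stop Criterion 2 adds that the exacerbation is extreme, refers back to the same behavior rule, and makes no exception for agreement. The overlap is therefore confined to extreme cases; for lesser shifts the restart clause stands alone. Extreme is not defined.

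**3. Week-36 safety labs**

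- Required: section 13 risk management, in two sentences.
- Weaker support: Laboratory evaluations in section 10 (blood at all six visits, with safety tubes in the volume quoted for each) and the visit table (week 36 is ticked, but one column combines safety and research blood).
- Left out: the section 8 timeline, and the three places in section 10 named above.

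**4. Blood volume if safety labs are run at week 36**

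Inputs: about 4 ml (liver, thyroid, renal), 1.5 ml (blood counts) and 7.5 ml (biomarkers) per visit, from Laboratory evaluations; limits of 2 ml/kg per draw and 3 ml/kg in 8 weeks; lowest weight in the dosing table, 30 lb.

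- Per visit: 4 + 1.5 + 7.5 = 13 ml; safety part 4 + 1.5 = 5.5 ml.
- Weeks 30 and 36 are 6 weeks apart, so both can fall in one 8-week window. Research blood only at week 36: 13 + 7.5 = 20.5 ml. With safety labs: 13 + 13 = 26 ml. With one 4 ml recheck as well: 30 ml.
- Weight: 30 / 2.2046 = 13.6 kg. Limits: 2 × 13.6 = 27.2 ml per draw; 3 × 13.6 = 40.8 ml in 8 weeks.
- Lowest weight that allows 26 ml: 26 / 3 = 8.7 kg (about 19 lb). For 30 ml: 30 / 3 = 10 kg (about 22 lb).

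The added tubes fit the limits at the lowest dosing weight.

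**The case against.** A reader might infer that the protocol tells staff to keep dosing a symptom-free child with out-of-limit labs. It does not. The list says to pause if its conditions are met, not only if they are met, and the labs-only pause is mandatory in four places, one of them in section 13 itself. Staff who follow the whole protocol always pause. Results come back the same day (section 21), and the visit texts call for DSMB advice before drug is resumed. This objection stands: the list is incomplete and misleading on its own, but it is not an opposing order.

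A reader might also infer that the behavior conflict is left without guidance. Section 10 has the principal investigator decide stoppage in consultation with the DSMB, and section 15 favors taking the child off treatment when parental support is lacking or clinical review suspects an unwanted effect. A mandatory, narrower rule would ordinarily prevail over a permissive one. These texts lean towards stopping, but none states that Stop Criterion 2 overrides the restart clause.

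Finally, week 36 does not lack an off-drug safety check. A physical examination, vital signs and questions about side effects are scheduled there either way. Only the laboratory part is in doubt, and no dosing decision depends on it because drug ends at week 30.

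**Conclusion.** The inconsistencies are real and worth correcting; their consequence is modest. The pause list is narrower than the rule the protocol applies elsewhere, the restart and stop clauses overlap for extreme behavior without stated precedence, and the only scheduled off-drug laboratory check is both required and left out.

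The number of children affected cannot be estimated. The documents give no rate of silent lab abnormalities or extreme exacerbations in children. Section 15 reports that no laboratory result was out of range in the earlier trial. That points to few cases, but the trial was small and enrolled adolescents and adults, so it does not settle the rate in children.

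A stronger reading, that these mismatches undermine the trial's analyses, is not supported. Power and alpha do not depend on them. Labs at weeks 7 and 15 are drawn in both arms whatever the symptoms, so the blinded-phase toxicity comparison is unaffected.

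The conclusion assumes that section 14 refers to the headed lists in section 13, which is the natural reading but is not spelled out.

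**What to change.** 1. Reword Pause Criteria 1–3 so that liver, renal or thyroid labs outside the limits at any scheduled or unscheduled test, with or without symptoms, trigger the 2-week pause and recheck. Add a separate line that a serious side effect reported at any time prompts safety labs. Simply deleting the symptom phrase would lose that link, which Criterion 3 now carries for events between visits.
2. In the section 13 behavior text and in Pause Criterion 6, state that the restart clause does not apply once Stop Criterion 2 is met, with the principal investigator and DSMB deciding whether an exacerbation is extreme.
3. Run the safety labs on the blood already drawn at week 36, and bring the section 8 timeline and the three section 10 texts into line with section 13.

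The cost is a wording amendment through the IRB and DSMB, plus about 5.5 ml of blood per child at week 36, within the stated limits. For staff who already follow the whole protocol, the first change adds no pauses.

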Foreseeable risks: No severe adverse events have been observed in any trial with sulforaphane. In the case of ASD, however, we will be vigilant for any possible behavioral regression that could signify an unwanted interaction with concurrent medications or cause undue distress for the participant or guardian. Given the delicate balance between real events of this sort and those that could be due to a “reverse placebo effect” in the case of parental anxiety about new treatment, home reports of exacerbation will be confirmed by clinical review. If parental support for continuation is lacking and/or clinical review indicates a suspected undesired effect, censorship is the ethical policy even if definite proof of mechanism is lacking or it is possible that a worsened behavioral outcome would be transient.

A previous randomized, double-blinded phase I study of repeated administration (3 doses per day for 8 days) of sulforaphane-containing Broccoli Sprout Extract in healthy volunteers found no problems with safety and tolerance⁷¹. Another cross-over clinical

trial designed to look into bioavailability of sulforaphane reported no serious adverse effects⁵⁸. Another animal study has shown that sulforaphane raised liver enzymes but only on very high dose of >500 µmol/day, which is much higher than our proposed dose⁷². We will be vigilant in treating subjects with autism, for behavioral regression that could signify an interaction with concurrent medications or other adverse effect.

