Visit	Informed consent, eligibility criteria (ADOS, Leiter-3)	Adverse event reporting	Medical history, vitals, physical exam	Autism symptom severity (OACIS-S, OACIS-I, ABC, SRS, Vineland Adaptive Behavior Scale)	Blood draw (LFTs, RFTs, TSH, CBC, HSP, mTor, Nerf), urine sample for isoprostanes	Study drug dispensing	Visit duration
Double blind phase (50% participants receive sulforaphane and 50% receive placebo)							
Screening/ baseline visit	X		X	X	X	8 weeks	~ 2.5 hours
3 week phone survey		X					~ 15 minutes

7 week visit		X	X	X	X	7 weeks	~ 1.5 hours
15 week visit		X	X	X	X	8 weeks	~ 1.5 hours
Open label phase (all participants receive sulforaphane)							
18 week phone survey		X					~ 15 minutes
22 week visit		X	X	X	X	7 weeks	~ 1.5 hours
30 week visit		X	X	X	X		~ 1.5 hours
36 week visit		X	X	X	X		~ 45 minutes

11) Data and Specimen Banking*

We plan to store leftover blood and urine samples in -80 C freezer in the Dept. of Pediatrics at UMass and the Cullman Chemoprotection Laboratory at Johns Hopkins for a period of 3 years after completion of the study. They will be accessed by the P.I. or study staff. The samples will continue to be de-identified and labeled with unique study I.D. numbers. The link between the study ID and identifiable information will only be accessible by the UMass personnel. At the end of 3 years the samples will be forever anonymized, and the link between study ID and identifiable information will be destroyed. We will make application to the IRB for any further studies to be conducted, by ourselves or others, using these specimens.

12) Data Management*

Statistical Analysis: The OACIS-I, SRS and ABC data will be analyzed in a mixed model ANOVA with fixed effects for visit, treatment group, and their interaction and random participant-specific intercepts. The effect of sulforaphane on mean change in OACIS-I, SRS and ABC total scores from baseline will be estimated using linear contrasts. Estimates will be unbiased if any loss to follow-up is missing at random, conditional on the observed data and our model assumptions. Significantly greater improvement from baseline in mean scores among participants randomized to sulforaphane based on a two-tailed test at $\alpha = 0.05$ will be taken as support of our primary hypothesis.

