Parents and/or guardians will be responsible for ensuring the timely and complete adherence to daily medication dosage. They will be asked to keep a log of the time of day and the number of capsules taken. They also will monitor for and report any adverse events, undesirable psycho-behavioral reactions throughout the duration of the study or until censorship, should that occur. Parents/guardians will be trained to ensure that the study medication is kept in the original, properly labeled, child-proof containers in a place that is secure from access by siblings, school mates, other children, mentally impaired adults, or pets. Any spilled or lost medication will be documented and reported so that replacement will ensure adherence to prescribed dosages. Parents/guardians will be reminded by telephone at-least 24 hours beforehand of their appointments. Those who miss an appointment will be contacted by telephone in order to elicit the cause and reschedule within one week.

16) **Potential Benefits to Subjects***

Potential benefits of sulforaphane may include demonstrable functional improvements in social responsiveness in subjects with autism. Treatment with sulforaphane may also increase mitochondrial function and decrease oxidative stress, both of which have been subjects of research in autism.

Current treatment standards for children with ASD include various therapy programs, including ongoing speech and language, occupational, physical and behavioral therapies. Many are also in special school programs with Individual Educational Plans. We anticipate that some of the children will be taking prescriptions of antipsychotic, antidepressant, antianxiety or stimulant medications. Approximately 10% will have a history of epilepsy and may be taking anticonvulsants. We will carefully evaluate each medication a subject is taking for potential interactions with sulforaphane. Subjects will continue to participate in their usual therapy programs.

Novelty: This trial of sulforaphane in children with autism provides a novel approach with a strong theoretical basis in clinical observations of the effects of fever in autism. Preliminary evidence from *in vitro* models supports the hypothesized cellular effects of sulforaphane on heat shock proteins Nrf2, mitochondrial functions, and the mTOR pathway.

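### An undefined censorship policy can end data collection in children suspected of behavioural worsening, and no stated follow-up rule covers them

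*Combined protocol and SAP*

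**What the plan says.** Section 15 (Risks to Subjects, Foreseeable risks) requires home reports of exacerbation to be confirmed by clinical review. It then sets the trigger: "If parental support for continuation is lacking and/or clinical review indicates a suspected undesired effect". In that case "censorship is the ethical policy even if definite proof of mechanism is lacking", and this applies even where the worsening might pass. The term is not defined.

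The adherence paragraph closing Section 15 has parents report adverse events and behavioural reactions "throughout the duration of the study or until censorship, should that occur".

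After a permanent stop for abnormal laboratory tests, Section 10 (7 week visit) adds "although we will ask them continue to be followed up in the study". The 15 and 22 week visits say the same, and Section 13 repeats it ("though they will still continue to be followed-up in the study"). After a seizure, Section 13 has the child followed for the rest of the study.

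For significant shifts in behaviour, Section 13 gives a two-week pause, resumption if the behaviour settles, and possible restart by agreement if it does not. "Otherwise, medication will not be restarted and we will ask that the family return the remaining study drug supply". Nothing is said about later visits. Section 14 (Withdrawal of Subjects) only points back to the pause and stop criteria.

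On missing data, Section 12 (Statistical Analysis) says "Estimates will be unbiased if any loss to follow-up is missing at random", conditional on the observed data and the model.

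**The concern.** Behaviour is both the reason for censoring and the efficacy outcome. If censoring ends observation, the children whose later OACIS-I, ABC and SRS scores may be lost are those suspected of doing badly, and their later adverse events may be lost too. Safety is Specific Aim 2, and behavioural regression is a risk that Section 15 promises to watch for.

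The randomised comparison has only two post-baseline assessments, at weeks 7 and 15. A child lost before week 7 has no post-baseline score from which a model could learn about the worsening. The plan has no analysis set, no sensitivity analysis for missing data, and no rule for counting such children in the Fisher responder analysis. By contrast, the responder results quoted from the earlier adult trial (Section 4) counted drop-outs as non-responders.

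**Working it through.** The plan gives no figure on this point to reproduce, so the check is first of the text and then an illustration of size.

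**Text, side by side**

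| Reason for stopping drug | Where | Follow-up stated? |
|---|---|---|
| Laboratory values still abnormal after 2 weeks | Section 10 visits at 7, 15 and 22 weeks; Section 13 | Yes |
| Seizure | Section 13 text and stop criterion 3 | Yes |
| Behavioural worsening | Section 13 text, pause criterion 6, stop criterion 2 | No |
| Suspected undesired effect or lack of parental support | Section 15 | No; *censorship* |

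- If censorship means leaving the study, outcome scores and adverse-event reports both end. This is the natural reading, because Section 15 sets censorship against the duration of the study.
- If it means only stopping drug, clinic visits may continue, but the sentence still lets parents' reporting end when drug ends.
- So on either reading some adverse-event reporting can be cut short. Outcome scores are lost only on the first.
- Section 15 applies even to worsening that may be transient. Section 13 pauses for two weeks and allows resumption. The two do not agree.

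**Size, by illustration**

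Inputs from Section 12 (Power Calculations): 50 children randomised 1:1, so 25 per arm; difference 4; SD 4.9; two-sided 0.05. Assumed, because the documents give no rate: k of 25 lost, all on sulforaphane and all the worst scorers (higher is worse). A mean of 1-to-7 ratings cannot have an SD above (7 − 1)/2 = 3, so the planning units are not the plain scale. The shares of the planned effect are more useful than the units.

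*Complete cases.* With q = k/25 and c = Φ⁻¹(1 − q), the arm mean shifts by SD × φ(c)/(1 − q). For k = 2: q = 0.08, c = 1.405, φ(c) = 0.1487, and 4.9 × 0.1487/0.92 = 0.79, which is 0.79/4 = 20% of the planned effect. False-positive rates come from 40,000 simulated t-tests with no true effect.

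*Two visits.* Weeks 7 and 15 were simulated with assumed correlation 0.7 or 0.5. The week 15 mean was estimated by regression on week 7 within arm, which is valid under missing at random. It stands in for the planned mixed model and is not identical to it.

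| k of 25 lost, sulforaphane only | Complete-case shift (share of 4) | False-positive rate | Two-visit bias, loss on unrecorded week 15 score (correlation 0.7 to 0.5) |
|---|---|---|---|
| 0 | 0 | 5.0% | 0 |
| 1 | 0.44 (11%) | 6.7% | 0.21 to 0.30 |
| 2 | 0.79 (20%) | 9.3% | 0.44 to 0.60 |
| 3 | 1.11 (28%) | 13.3% | 0.62 to 0.84 |
| 5 | 1.71 (43%) | not run | 1.05 to 1.32 |

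All shifts favour sulforaphane. When loss instead depended on the recorded week 7 score, the two-visit bias was between −0.02 and 0.03, effectively zero. With the worst 2 removed from each arm, the complete-case mean bias was about 0.01, though the test still rejected 7.4% of the time.

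**The case against.** Several stronger conclusions are tempting, and the documents do not support them.

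- *The protocol orders bad outcomes to be removed.* It does not say so. Censorship is undefined, and Section 15 speaks of support for continuing in the context of anxiety about a new treatment, which fits stopping drug. The reporting sentence sits among parents' home duties. The Section 10 visit table lists adverse-event reporting and the outcome scales at every post-baseline visit, without exception.
- *The worsening is never recorded.* The triggering event is reported and clinically reviewed under Section 15. Under Section 13 the child is examined and the DSMB notified. Scores already collected are kept. Only later data are at risk.
- *The follow-up rule is contradicted.* It is written for laboratory stops and seizures and is silent on behavioural stops. That is a gap. The direct conflict is between Sections 13 and 15 on handling worsening.
- *Missing at random fails by design.* Section 12 states it only as a condition, and it can hold if recorded scores explain the loss, as the week 7 result shows.
- *The 12 to 19 percent in Section 15 is a censoring rate.* It covers a mixed list including vomiting, fever and headache, with the same incidence on placebo (P > 0.10).

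Phase 1 is also blinded, which makes differential censoring less certain. These objections narrow the point but leave the undefined term, the permission to stop reporting, the missing follow-up statement and the absence of any sensitivity analysis.

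**Conclusion.** The concern holds as a gap in the plan. Following the text as written can cut off later outcome and adverse-event data in children suspected of worsening, and nothing separates stopping drug from leaving the study.

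Bias in the week 15 contrast needs three things together: loss before week 15, a difference between arms, and a cause not captured by recorded scores. Worsening that arises between visits, or before week 7, makes the third plausible. Missing at random is then doubtful, and the plan does not test it. Censoring after week 15 leaves the randomised comparison alone but still affects safety counts and open-label data.

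Under the assumed one-sided loss of 1 to 3 of 25, an estimator valid under missing at random is biased by about 0.2 to 0.8 units, or 5% to 21% of the planned difference (0.21/4 to 0.84/4). These figures are illustrative, because the documents give no censoring rate. The change should be made; confidence is medium because it depends on how an undefined word is read.

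**What to change.** 1. In the adherence paragraph of Section 15, delete censorship as an end point for adverse-event reporting.
2. In Section 14, state that a child whose study drug is paused or stopped for any reason keeps the scheduled OACIS-I, ABC, SRS and adverse-event assessments through week 36, unless consent is withdrawn, and is analysed as randomised.
3. In Section 12, add one sensitivity analysis. Children lost after reported worsening before week 15 are scored as worsened, with values fixed in advance (for OACIS-I, on the worse side of 4), and count as non-responders in the Fisher analysis.
4. The sponsor must define censorship and reconcile Section 15, which applies it even to possibly transient worsening, with Section 13, which pauses for two weeks and may resume. No clinical stopping rule is proposed here.

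The cost is wording changes, some extra effort to retain families who have stopped drug, and a little analysis work. The visits are already in the schedule.
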